b. Study visit 3

Study visit 3 is for the performance of the Lexercise stress Rubidium-82 or N-13 ammonia PET study. This will be scheduled at least the next calendar day or within 2 weeks of the Visit 2 rest/stress scans. While we aim to conduct the Visit 3 “Lexercise stress” scan within two weeks of the 2 rest/stress scans, if there is a scanner malfunction or patient schedule conflict, we would like to extend the time frame for enrollment to 4 weeks. Approximately 5 cc of blood will be drawn following completion of the Rubidium-82 or N-13 ammonia imaging study for troponin levels. Blood samples will not be drawn for micro RNA measurements in the healthy volunteer cohort.

Detailed Description of PET MPI Methods: The proposed research will utilize the resources of the Cardiovascular Imaging center at Brigham and Women’s Hospital, Boston MA. Specifically, PET imaging will be performed on a state-of-the-art 64 slice cardiac PET/CT unit.

Before the test: All patients scheduled for a rest- vasodilator stress Rubidium-82 PET or N-13 ammonia will receive written instructions to fast overnight, avoid caffeine containing beverages and medications for 24 hours prior to the test and bring all their medications (including prescription, over the counter, dietary supplements, herbal and vitamins) with them. Upon arrival for the test, all patients are given a written questionnaire about allergies and possibility of pregnancy (women of child bearing age will undergo a blood pregnancy test prior to the rest Rubidium-82 or N-13 ammonia PET study), as per laboratory protocol. Patients without objection will be detailed about the study and related procedures and

consenting patients will be recruited into the study. An experienced exercise physiologist/imaging fellow obtains a detailed clinical history from each patient and confirms it by a review of electronic medical records. Written informed consent for the study is checked and IV line inserted, ECG module connected and the patient brought into the PET/CT room for imaging. A detailed datasheet will be used to record information on demographics, history on coronary risk factors, reason for the test, nature of symptoms (chest pain type, shortness of breath description), resting ECG interpretation (as approved by a cardiologist), list of medications, resting and stress hemodynamics, dose of Lexiscan, dose of Rubidium-82 or N-13 ammonia injected, reason for test termination, symptoms and ECG changes during stress test.

Rubidium-82 or N-13 ammonia PET image acquisition:

Following skin preparation and ECG lead placement, patient undergoes a symptom limited standard Bruce exercise treadmill test. At peak exercise (when patient is unable to exercise for more than 1 minute), the treadmill is stopped and patient is immediately positioned on the imaging table. Image acquisition is started with a CT scout image for positioning the heart (10 mA, AP scout, 9 seconds). Then 0.4 mg of regadenoson is given by intravenous push over 10 seconds followed by 10 ml of normal saline flush. Right after the saline flush, 40-60 mCi of Rubidium-82 or 20 mCi of N-13 ammonia is injected and emission imaging started in a list mode fashion started at the time of injection of radiotracer. Following completion of the emission imaging, a CT transmission scan (20 mA, 120 KV, non-gated, free tidal breathing) is obtained for correction of photon attenuation by soft tissues. .

Rest and Lexiscan stress images from the clinical study and the Lexercise stress emission images will be unlisted for analysis into a static file, a gated file and dynamic image frames (36 frames of 5 seconds each, 8 frames of 15 seconds each, and 6 frames of 30 seconds each for stress and 2 groups for rest of 24 frames at 5 seconds each and 8 frames at 30 seconds each). In subjects with serious or bothersome adverse effects, aminophylline will be administered intravenously (1 mg/kg, to a maximum of 150 mg) to alleviate the symptoms.

Myocardial blood flow quantification:

Myocardial blood flow (in ml/gm/min) at rest and after vasodilator stress will be quantified using a software based on GFADS and a 2 compartment model, developed and validated at the Brigham and Women's Hospital.¹³ Rest and peak stress myocardial blood flow will be computed in ml/gm/min and global and regional (vascular territories assigned as described below) coronary flow reserve computed by dividing stress myocardial blood flow by rest myocardial blood flow. Coronary vascular resistance at rest and stress will be computed by dividing mean aortic pressure [derived as 2 (diastolic blood pressure) + systolic blood pressure/3] by myocardial blood flow. In addition to calculating the myocardial blood flow for the left ventricle as a whole, myocardial blood flow will be determined for each of three vascular beds

(left anterior descending [LAD], left circumflex [LCx], and right coronary artery [RCA]). Subendocardial and subepicardial myocardial blood flow will be assessed globally.

Interpretation of relative myocardial perfusion images:

The semi-quantitative clinical interpretation of Rubidium-82 or N-13 ammonia images will be performed using a standard 17 segment model and a 0-4 scale (0=normal, 1= mild defect, 2=moderate defect, 3=severe defect, 4= absent radiotracer uptake). The sum of the scores in the 17 segments at stress and rest will be computed as the summed stress score (SSS) and summed rest score (SRS) respectively. The summed difference scores (SDS) will be derived as SSS – SRS. The SSS, SRS and SDS will be converted into percentages to compute total percent myocardium abnormal, scarred or ischemic determined as $(100/68)*SSS$, $(100/68)*SRS$ or $(100/68)*SDS$, respectively. Perfusion defects on relative PET will be assigned vascular distributions as described previously.¹⁴ LV volumes and EF will be estimated using FDA approved software (EcTb), with automatic edge detection and manual refinement when needed.

Interpretation of absolute myocardial perfusion images:

Myocardial blood flow at rest, stress and CFR are calculated for the left ventricle as a whole, as well as for each of three vascular beds (left anterior descending [LAD], left circumflex [LCx], and right coronary artery [RCA]). Polar plots of CFR will be generated and defect extent and severity computed in relation to a quantitative CFR normal limits database (developed at BWH).

Study Endpoints Assessed:

- Diagnostic value:
 - Defect size, severity, extent and contrast with Lexiscan alone compared to exercise Lexiscan protocol
 - Left ventricular ejection fraction at rest and immediately post stress will be compared in the Lexiscan alone and the exercise Lexiscan protocol.
 - Myocardial blood flow estimates and coronary flow reserve will be compared between the Lexiscan alone and Lexercise protocols.
 - Comparison to coronary angiography results when available.
- Safety and tolerability:
 - Side effects, ECG changes, blood pressure changes, will be recorded.
 - Safety blood work will be drawn after the Lexiscan and the Lexercise PET study to measure serum troponin T levels.
 - Radiation dose to the staff will be measured using personal dosimeters after the Lexiscan as well as the Lexercise PET study.
- Image quality:

- Motion artifacts
- Image registration
- Sub diaphragmatic activity (liver heart ratios)
- Defect contrast
- Signal to noise ratio and
- Dynamic image evaluability will be assessed

VI. BIOSTATISTICAL ANALYSIS

The overall aim of this pilot study of 50 patients is to assess the tolerability, safety, diagnostic accuracy and image quality between Lexiscan with symptom limited exercise compared to Lexiscan alone.

Aim 1. For this aim, we will compare the reported side effect profile for Lexercise to Lexiscan PET, using a Pearson Chi square test. A P-value of <0.05 will be considered significant.

Aim 2: For this aim, we will compare objective measures of image quality including signal to noise ratio using dynamic Rubidium-82 images or N-13 ammonia, the frequency of misregistration between PET and CT, the frequency of presumed motion artifact and bowel radiotracer activity. These measures will be compared using a student's t-test or a Pearson Chi square test, as appropriate. A P-value of <0.05 will be considered significant.

Aim 3: For this aim, we seek to compare measures of semi quantitative relative perfusion, absolute perfusion and LVEF using the Lexiscan alone compared to Lexercise PET. Firstly, we will compare semi-quantitative defect size, severity and reversibility between the Lexercise and Lexiscan PET studies. Based on the results of one prior study using N-13 ammonia and comparing dipyridamole versus treadmill exercise², a sample size of 35 subjects with reversible defects should be adequate to identify if significant differences exist between Lexercise and Lexiscan PET protocols. Next, we will study the changes in LVEF from rest to peak stress in Lexercise versus Lexiscan PET studies in the normal and ischemic subjects. Finally, we will compare regional rest and peak stress myocardial blood flow and coronary flow reserve between Lexercise and Lexiscan PET studies.

VII. RISKS AND DISCOMFORT

Time: Participation in this trial entails an exercise vasodilator stress Rubidium-82 PET or N-13 ammonia scan. The total time spent for the study procedures is approximately 1 hour.

Intravenous line insertion: Possible side effects intravenous line insertion are pain, bruising, or infection where the needle entered the skin. Some people faint or get dizzy during insertion of the intravenous line.

Radioactive imaging agents may have the following side effects: The average dose from the research radiation is approximately 2.7 mSv, which is approximately 6% of the amount allowed per year for a person who routinely work with radiation sources. For healthy volunteers, the average dose from the research radiation is approximately 6.9 mSv, which is approximately 13.8% of the amount allowed per year for a person who routinely work with radiation sources. Other side effects include: metallic taste in the mouth, burning at the injection site, facial swelling, numbness of the hand and arm, low blood pressure, nausea, angina and chest tightness. Radiation exposure associated with both rest and stress imaging is well within acceptable safety standards as set forth by the FDA. Radiation may cause physical or genetic damage to a fetus, so subjects that are pregnant or breast feeding will be excluded. A pregnancy test will be performed prior to enrolling patients with childbearing potential.

Lexiscan: In previous studies where vasodilator stress agents were given to patients with heart disease at the FDA approved doses, they have been reported to be associated with the following side effects including dyspnea-shortness of breath (28%), headache (26%), flushing (16%), chest discomfort (13%), angina pectoris-chest pain caused by myocardial ischemia (12%), dizziness (8%), chest pain (7%) and nausea (6%), flushing, feeling of heat, hypoesthesia (decreased sensitivity), paresthesia (tingling of the arms and legs), sensation of heaviness, abdominal pain, palpitations, unpleasant taste in the mouth and feeling hot (each 5%). Increases in heart rate and mild decreases in blood pressure have also been associated with administration of vasodilator stress agents.

In addition to the risks or discomforts listed above, the study drug and procedures may have unknown side effects. There is always the possibility that subjects will have a reaction that is currently not known or not expected. All drugs can cause an allergic reaction that, if not treated promptly, could be life-threatening. Symptoms of such a reaction are: throat tightness, itching, hives ,wheals ,vomiting ,difficulty breathing or turning blue.

Risks of withholding medications: Certain medications such as beta-blockers, nitrates, diuretics, calcium channel blockers and bronchodilators may have to be held for 12-24 hours prior to the study. Withholding these medications may result in chest pain or angina, high or uncontrolled blood pressure, high blood glucose, or in very rare instances a heart attack. For these reasons we will only enroll subjects that are clinically stable without uncontrolled angina, hypertension or are acutely ill for any reason. The medications that will be withheld and the length of the time withheld are shown below. To minimize the

risk, the prescribing physician will be consulted to give permission for his patient to withhold the specified medication for the specified length of time.

Hold on the morning of the test

Diabetic agents: Insulin Half of Normal Morning Dose can be taken.

Hold oral Hypoglycemics till after the test completion: Actos, Amaryl, Avandamet, Avandia, Avandaryl, Byetta, Diabeta, Diabinese, Fortamet, Glipizide, Glucophage, Glucovance, Glucotrol, Glyburide, Metformin, Micronase, Prandin

Hold 4-6 hours prior to testing

Nitroglycerine, Deponit, Nitro-Bid, Nitro-Disc, Nitro-Dur, Nitro-Gard, Nitrol, Nitrostat, TransdermNitro, Trasdermal-NTG, Nitro paste

Hold 12 hours prior to testing

Nitro-
Nitrates, Isosorbide Dinitrate Isordil, Dilatrate, Sorbitrate, Isosorbide Mononitrate, Imdur, Ismo, Monoket

Hold 24 hours prior to testing

Bronchodilators Aerolate, Aminophylline, Aquaphyllin, Asmalix, Choledyl, Elizophylline Slo-bib, Slo-Phyllin, Thoe-Dur, Theovent

Calcium Channel Blockers

Amlodipine Cauduet, Lotrel, Norvasc, Diltiazem Cardizem CD, Cardizem SR, Cartia XT, Dilacor XR, Diltia XT, Tiazac, Taztia XT, Felodipine Plendil, Isradipine DynaCirc, Nicardipine, Hydrochloride, Cardene, Cardene SR, Nifedipine Adalat, Adalat CC, Procardia, Procardia XL
Nimodipine Nimotop, Nisoldipine Sular, Verapamil, Hydrochloride, Calan, Calan SR, Covera, Isoptin, Isoptin SR, Verelan

Miscellaneous

Cafergot, Cialis, Levitra, Ranexa, Ranolazine, Trental, Pletal, Viagra.

Hold 48 hours prior to testing

Dipyridamole, Persantine, Aggrenox

Aminophylline: Side effects of aminophylline may include nausea, headache, restlessness, convulsions, rapid breathing, a rapid heart rate, and allergic reactions such as rash.

VIII. POTENTIAL BENEFITS

No direct benefit is anticipated to individual subjects. The results of this study may benefit society through evaluation of the diagnostic utility of novel protocol utilizing combined symptom limited exercise vasodilator stress test to image endothelium dependent and endothelium independent factors affecting myocardial blood flow.

IX. MONITORING AND QUALITY ASSURANCE

Subject safety will be ensured by strict adherence to inclusion and exclusion criteria and close monitoring. Subjects that experienced serious adverse events during the study will be removed from the study and followed up, but no other study procedures will be performed. We will monitor the subjects closely for seizures and ischemic symptoms. History of seizures is an exclusion criteria for the study. Individuals who experience seizures for the first time during the initial regadenoson study will be excluded from the second regadenoson with exercise study. Intravenous aminophylline, a competitive agonist, will be administered for ischemic symptoms. Subjects with ischemic symptoms will be monitored until complete resolution (current clinical practice). As listed in page 22, study endpoints, safety blood work will be drawn after the Lexiscan and the Lexercise PET study to measure serum troponin T levels. This study does not involve treatment and hence a data safety monitoring board.

This is a pilot clinical study of about 50 subjects. The study PI, [name], will be responsible for monitoring the study procedures after every subject is enrolled, including the accuracy and completeness of the case report form entries, source documents and informed consent after every enrollment. These documents will be appropriately maintained on submission.

Specification of Source Documents

The following information will be included in the source medical records:

- Demographic data (age, sex, and race)
- Inclusion and exclusion criteria details
- Participation in study and signed and dated informed consent forms
- Visit dates
- Medical history and physical examination details
- Key efficacy and safety data
- Adverse events and concomitant medication
- Results of relevant examinations
- Laboratory printouts
- Reason for premature discontinuation

Ethical Conduct of the Study

The investigator(s) and all parties involved in this study will conduct the study in adherence to GCP, ICH Guidelines and the applicable laws and regulations.

Subject Confidentiality

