This is a single-center, prospective cohort study of subjects undergoing clinically indicated PET/CT MPI, with documented coronary artery disease or an intermediate to high pretest likelihood of coronary artery disease. Following the clinical study, the research study is explained to the subjects. Consenting subjects will return on another day (next calendar day or later) for a repeat stress study with Lexercise or a repeat Lexiscan stress PET. Approximately 50 subjects (not more than 16 patients with normal Rubidium-82 or N-13 ammonia PETMPI, 10 healthy volunteers and 24 patients with reversible perfusion defects) will be enrolled in this study. After successful screening and enrollment, 13 random subjects (8 normal and 5 ischemic) will return for repeat Lexiscan PET, and 37 subjects will return for a Lexercise PET/CT MPI. Lexiscan PET will be performed per standard protocol. For Lexercise, a symptom limited exercise treadmill study with Lexiscan injection at peak exercise is performed. Rubidium-82 or N-13 ammonia will be injected and PET/CT images will be obtained in a list mode acquisition. Images will then be unlisted and myocardial blood flow computed.

Number of Subjects Planned

Approximately 50 subjects will be enrolled into the study.

Main Selection Criteria

Subjects will be eligible if they meet all of the following inclusion criteria and none of the exclusion criteria:

Inclusion criteria:

- Age > 18 years
- Clinically indicated Rubidium-82 or N-13 ammonia PET study
- Ten healthy volunteers recruited using web based advertisements.
- Known coronary artery disease (prior percutaneous coronary intervention, prior coronary artery bypass surgery or Q wave MI on ECG) or intermediate to high pretest likelihood of CAD
- Able to exercise on a treadmill
- Able and willing to provide informed consent to participate in the study

Exclusion criteria:

- Contraindications to exercise stress testing such as
 - unstable angina
 - known severe left main coronary artery stenosis
 - severe or uncontrolled heart failure
 - uncontrolled atrial or ventricular arrhythmias
 - symptomatic hypotension or severe hypertension (systolic blood pressure < 90 or > 200 mmHg, respectively)
 - > 1st degree atrioventricular block in the absence of a functioning pacemaker.
- Contraindications to Lexiscan use such
 - Allergy or intolerance to aminophylline or regadenoson

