- Hospital in-patients with request for pharmacologic stress: Attending physicians will be asked if they felt comfortable introducing the study to their subjects that they schedule for in-patient pharmacologic stress myocardial perfusion study verbally during their visit. If the physician introduces the study verbally, the subject will be asked if they would like to speak with a coordinator after the visit. If they would like to speak with someone, the coordinator will be notified and they will explain the study to the subject and go over the inclusion and exclusion criteria for the study. If they are interested in participating in the study an appointment will be made for their first visit.
- Special attention will be paid to enroll women and minorities in the study.
- Ten healthy volunteers will be recruited for this study using web based advertisements. They will all undergo Lexiscan (regadenoson) followed by Lexercise protocol (exercise + regadenoson) on a separate day.

b) Procedures for obtaining informed consent (including timing of the consent process)

For subjects interested in speaking to a study staff, Study PI, will go over the inclusion and exclusion criteria and will describe the study and procedures to the potential subject over the phone or in person. If the subject qualifies and is interested he/she is encouraged to discuss the study with his/her primary care physician or family members. Upon arrival for the study, the subject will be given a copy of the consent form to read. After the subject has finished reading the consent form, one of the physician investigators will describe the study in detail and answer any questions or concerns

the subject might have. If the subject agrees to participate in the study they will be asked to provide his/her written informed consent. Subjects will be given a copy of the signed consent form for their records. The investigator will inform the subject that they have the alternative not to participate in the study and can withdraw their consent at any point during the study.

The subjects will be given as much as 2 weeks to consider participation in the trial. Pregnant women and minors are excluded from this trial. Subjects that are determined by the physician to be unable to consent due to their physical or mental condition will not be enrolled in this trial.

V. STUDY PROCEDURES

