The patient will have 1-2 study visits and healthy volunteers will have 2-3 study visits. Study visit 1 is the same for patients and healthy volunteers.

a. Study visit 1

- a. The subjects that are interested in the study will meet with [name] and go over the consent form and details of study participation.
- b. This screening visit will take about 1 hour. The research study team will ask the subject questions about medical history, medications, and prior hospitalizations to make sure that the subject qualifies for this study. Blood pressure, heart and breathing rates, temperature, and height and weight will be measured. Pregnancy is not allowed due to the unknown risks radioactivity may have on the mother or the unborn baby from the beginning of the study period through the end of the study. A blood pregnancy test will be performed on the day of the PET scan in women with child bearing potential.

Patients:

a. Study visit 2

The study visits 1 and 2 can be conducted on the same day. Study visit 2 is for the performance of the Lexercise stress Rubidium-82 or N-13 ammonia PET study. This will be scheduled at least the next calendar day or within 2 weeks of the clinical Rubidium-82 or N-13 ammonia PET study. While we aim to conduct the research scan within 2 weeks of the clinical scan, if there is a scanner malfunction or patient schedule conflict, we would like to extend the time frame for enrollment to 4 weeks.

Approximately 20 cc of blood will be drawn following completion of the Rubidium-82 or N-13 ammonia imaging study and evaluated for biochemical markers of ischemia.

b. Study Visit 3

Study visit 3 is for the performance of the Lexercise stress Rubidium-82 or N-13 ammonia PET study. This will be scheduled at least the next calendar day or within 2 weeks of the clinical Rubidium-82 or N-13 ammonia PET study. Approximately 20 cc of blood will be drawn following completion of the Rubidium-82 or N-13 ammonia imaging study and evaluated for biochemical markers of ischemia. A part of this blood sample (10 cc) will be sent to the laboratory of [name] for the isolation of microRNAs involved in angiogenesis and vascular inflammation. This blood sample will be stored for future analysis.

Healthy volunteers:

a. Study visit 2

The study visits 1 and 2 can be conducted on the same day. Study visit 2 is for the performance of the rest and regadenoson stress Rubidium-82 or N-13 ammonia PET study. No blood drawing will be performed during this visit.

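### Troponin T is promised after both the Lexiscan and the Lexercise study, but the schedule rules it out at the volunteers' Lexiscan visit, leaves it unclear for patients, and includes no pre-stress sample

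*Combined protocol and SAP*

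**What the plan says.** Study Endpoints Assessed, under safety and tolerability, states: "Safety blood work will be drawn after the Lexiscan and the Lexercise PET study to measure serum troponin T levels". Section IX (Monitoring and Quality Assurance) repeats the commitment: "safety blood work will be drawn after the Lexiscan and the Lexercise PET study to measure serum troponin T levels".

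The blood draws themselves are set out visit by visit in section V (Study Procedures):

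- **Volunteers, visit 2 (rest and Lexiscan):** "No blood drawing will be performed during this visit".
- **Volunteers, visit 3 (Lexercise):** "Approximately 5 cc of blood will be drawn following completion of the Rubidium-82 or N-13 ammonia imaging study for troponin levels".
- **Patients, visits 2 and 3:** about 20 cc each time, where "blood will be drawn following completion of the Rubidium-82 or N-13 ammonia imaging study and evaluated for biochemical markers of ischemia". Troponin is not named, and both visits are described as Lexercise.

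On who has which study, section IV says of the ten volunteers: "They will all undergo Lexiscan (regadenoson) followed by Lexercise protocol (exercise + regadenoson) on a separate day". For the return visits, the Synopsis says: "13 random subjects (8 normal and 5 ischemic) will return for repeat Lexiscan PET, and 37 subjects will return for a Lexercise PET/CT MPI". The patients' first Lexiscan study is the clinical scan.

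**The concern.** Aim 1 compares the safety of Lexercise with that of Lexiscan alone, and troponin T is the one laboratory safety measure listed for both studies. If the visit schedule is followed, the volunteers will have a value after Lexercise and none after Lexiscan. They are the one group whose two studies both fall within scheduled study visits. For patients, it is not clear that any draw is tied to a Lexiscan study.

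There is also no sample before stress. Many of these subjects have known coronary disease. The exclusions for dialysis and for recent infarction, coronary intervention or bypass surgery remove some reasons for a raised starting value, but they do not supply one. A raised result after Lexercise could have been present before the treadmill started.

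**Working it through.** No test, power figure or sample size is at issue. The check sets the promised draws against the scheduled ones and counts subjects.

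**Step 1. Reproduce the allocation (Synopsis).** Patients: 16 normal + 24 with reversible defects = 40. Section IV gives all 10 volunteers Lexiscan and then Lexercise, so the 13 repeat-Lexiscan subjects must be patients. Lexercise patients: 40 − 13 = 27. Lexercise in total: 27 + 10 = 37, which matches the Synopsis. Section III gives 34 instead of 37; the zeros below do not depend on which is used.

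**Step 2. Scheduled draws by group (section V).**

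| Group | n | Before stress | After Lexiscan | After Lexercise |
|---|---|---|---|---|
| Volunteers | 10 | 0 | 0 (ruled out) | 10, troponin named |
| Lexercise patients | 27 | 0 | 0 written for the clinical scan | 27, ischemia markers, troponin not named |
| Repeat-Lexiscan patients | 13 | 0 | 0 if both labels are literal; up to 13 if one is a slip | not applicable |

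**Step 3. Count what can be compared.**

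- Scheduled Lexiscan and Lexercise values in the same subject: 0 of 10 volunteers + 0 of 27 patients = 0 of 37 (0 of 34 on the section III count).
- Scheduled values before and after stress in one session: 0 of 50.
- Lexiscan values in anyone: 0 to 13. Any that exist come from people who do not have Lexercise, so among patients they support only a between-subject comparison.

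**Step 4. Timing.** The only anchor is the end of imaging. The stress frames listed under image acquisition add up to 36 × 5 + 8 × 15 + 6 × 30 = 480 seconds. A draw about 8 minutes after tracer injection, plus the CT, would therefore comply. No fixed interval is given that would make draws comparable across studies.

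**Step 5. How many subjects new draws could reach.** The cover page gives enrollment as June 2010 to June 2017, which is 84 months. From this version (September 2016) about 9 remain. The documents give no accrual figures. If accrual were even (an assumption), 9/84 × 37 ≈ 4 Lexercise subjects and 9/84 × 10 ≈ 1 volunteer would be left. Without that assumption the range is 0 to 37.

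**The case against.** **The patient gap may be a labelling slip.** Patient visits 2 and 3 are described by the same sentence, nothing gives a patient two Lexercise studies, and 13 patients must return for Lexiscan somewhere. One label is probably meant for repeat Lexiscan, and both visits carry a post-imaging draw. This stands. A reader might infer that troponin is drawn after Lexercise only, in everyone; the documents do not support that for patients. The slip does not help the volunteers, whose Lexiscan visit excludes blood in plain words.

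**Patients could be sampled at the clinical scan.** The Synopsis says "Following the clinical study, the research study is explained to the subjects", which suggests that consent always comes too late. But section IV has the referring physician introduce the study before the clinical scan as the main route, and the text under Before the test describes consent on arrival for a vasodilator scan. So the tempting reading that a same-subject comparison is possible only in the 10 volunteers is not supported. What remains is that no such draw is written in the visit schedule.

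**No troponin analysis is promised.** This is correct. Section VI plans a chi-square test on reported side effects for Aim 1, and troponin appears only as safety blood work. It would be wrong to say that a planned test has been lost. The pre-stress sample and fixed draw time are cheap improvements, not something that the plan committed to and omitted.

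**Early draws are uninformative.** A reader might go on to say that a negative value right after imaging means nothing. That depends on the assay, which the documents do not give.

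**Conclusion.** The point holds as an internal inconsistency in one safety endpoint. It is firm for the volunteers: 0 of 10 can have the Lexiscan troponin value that two other sections promise. For patients it is a matter of unclear text: no draw is written after the clinical scan, and at most 13 have a draw after repeat Lexiscan, none of them among the 27 who have Lexercise. The lack of any pre-stress sample (0 of 50) means that a raised value after Lexercise cannot be assigned to the session.

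The counts rest on the Synopsis numbers and on section IV's statement that every volunteer has both studies. The figure of 13 also assumes that the label is a slip and that troponin T is among the patients' ischemia markers.

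The consequence is limited to troponin. Side effects, ECG and blood pressure are recorded separately and are not affected. Nor should a correction be presented as giving a troponin change in all 37 Lexercise subjects: at this date it can reach only those not yet studied.

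**What to change.** **1. Make the schedule and the endpoint agree.** Choose one:

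- In section V, delete the sentence that rules out blood at the volunteers' Lexiscan visit and draw about 5 cc for troponin T there. Correct the patient visit label so that the 13 repeat-Lexiscan subjects have a troponin T draw, and name troponin T in the patient draws.
- If Lexiscan draws are not wanted, state in Study Endpoints Assessed and in section IX that troponin is assessed after Lexercise only.

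**2. For remaining subjects, make the value interpretable.** Add one pre-stress troponin T tube through the IV line already placed, use the same post-stress draw time at both studies, and report the change. Where a patient consents before the clinical Lexiscan scan, allow a draw after it, so that a same-subject comparison is not confined to volunteers.

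**3. For subjects already studied,** state in the report which troponin values exist, by group and by study.

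**Cost.** No extra visit. At about 5 cc per tube:

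- Lexercise patient: 1 pre-stress tube = 5 cc; up to 15 cc if a pair is also taken at the clinical scan (5 + 2 × 5).
- Repeat-Lexiscan patient: 5 cc, or 10 cc if the existing post-imaging draw does not already apply.
- Volunteer: a pair at Lexiscan plus one pre-stress tube at Lexercise, 2 × 5 + 5 = 15 cc.

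The Lexercise-only wording in item 1 costs no blood; with item 2's pre-stress tube it comes to 5 cc per Lexercise subject.
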